5.3 Study Visits

5.3.1 Pre-Treatment

The following assessments should be performed on Day 0 prior to the first dose preferably in the following order:

- Informed consent
- Inclusion/exclusion criteria
- Medical history
- COVID-19 infection history (SARS-CoV-2 variant information to also be collected if available)
- Patient demographics
- Physical examination (chest examination only unless a physical examination is deemed necessary by the Investigator)*
- WHO OSCI*
- Height and weight
- Vital signs (to include temperature, respiratory rate, heart rate and blood pressure)*
- BCSS
- NEWS2 (the highest NEWS2 score for each calendar day should be collected)
- EQ-5D-5L (complete questionnaire)
- Height and weight
- Urine pregnancy test, if applicable
- Check the patient will be able to use the nebuliser
- Randomisation
- Blood sample for immunogenicity test (all sites/patients, where collection is feasible)
- Recording of AEs, SAEs and concomitant medications

*Physical examination, WHO OSCi, and vital signs assessments should be conducted together at approximately the same time each day.

Eligibility to enter the study may be aided with data captured from SOC procedures and tests performed as part of the admission process.

Patients may take the first dose of study medication either on the same day as the pre-treatment assessments or the next day depending on timings. Day 1 is the day the first dose of study medication is taken. If Day 1 is the same as the day the pre-treatment assessments are performed then the Day 1 assessments do not need to be repeated.

5.3.2 Days 1 to 14

The following assessments should be performed daily from Day 1 to 14.

For patients that remain in hospital the following assessments should be performed preferably in the following order:

- WHO OSCI*
- Physical examination (chest examination only unless a physical examination is deemed necessary by the Investigator)*
- Vital signs (to include daily temperature, respiratory rate, heart rate and blood pressure)*
- BCSS
- EQ-5D-5L (complete questionnaire on Day 7 only. Mobility, self-care and usual activities dimensions from Day 1 to Day 14)
- COVID-19 symptom assessment
- NEWS2 (the highest NEWS2 score for each calendar day should be collected)
- Device training (if required)
- Administration of study medication
- Recording of AEs, SAEs and concomitant medications.

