6.6 Ordinal Scale for Clinical Improvement

The OSCI to be used in this trial is the 18 February 2020 version as recommended by the WHO (7).

Ordinal Scale for Clinical Improvement

Patient State	Descriptor	Score
Uninfected	No clinical or virological evidence of infection	0
Ambulatory	No limitation of activities	1
	Limitation of activities	2
Hospitalised	Hospitalised, no oxygen therapy	3
	Oxygen by mask or nasal prongs	4
Hospitalised	Non-invasive ventilation or high-flow oxygen	5
	Intubation and mechanical ventilation	6
	Ventilation + additional organ support – pressors, RRT, ECMO	7
Dead	Death	8

RRT – renal replacement therapy; ECMO - extracorporeal membrane oxygenation

The assessment should be carried out once a day at approximately the same time each day from Pre-treatment until Day 35. It is recommended that this assessment should be carried out by a clinically qualified member of the study team, i.e. a medical doctor or a qualified nurse. The assessment may be carried out face to face (before discharge) or over the phone/video link (post-discharge).

Patients' status on the day of hospital discharge should be assessed as ambulatory/uninfected (WHO OSCI score of 0, 1 or 2).

On the day of hospital discharge and on the days following hospital discharge, patients should be asked the following questions about their clinical status and return to the pre-COVID-19 level of activity:

- “In the past 24 hours, did you experience any signs or symptoms of your coronavirus infection?” “Yes” or “No” answer will be required.
- “In the past 24 hours, did you feel that your usual activities (e.g. work, study, housework, family or leisure activities) have returned to the level from before your coronavirus infection and did not require additional assistance/support*?” “Yes” or “No” answer will be required.

* assistance/support is defined as additional help of other people and/or requirement for supplemental oxygen (or a higher level of supplemental oxygen), compared to the pre-COVID-19 state.

In order to minimise any potential influence on the patients, the interviewers will be required to read the questions to patients verbatim and not to change or interpret them in any way. The following scoring algorithm will be applied:

Presence of signs/symptoms of coronavirus infection (or virological evidence of infection)?	Usual activities returned to baseline level?	WHO OSCI score
No	Yes	0
Yes	Yes	1
No	No	2
Yes	No	2

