The result of the OSCI assessment, from the day of hospital discharge, must be based upon the patient's responses to the 2 questions specified above and must not be adjusted based on the results from other outcome assessments (e.g. BCSS, brief pain inventory, long COVID-19 symptom assessment, and EQ-5D-5L), even if these data provide conflicting clinical information.

Repeated assessments of virological clearance in patients discharged from the hospital are not feasible within the study. Patients discharged from the hospital will be considered to have no virological evidence of infection unless a positive test is obtained.

The applicable WHO OSCI score and the date of assessment should be recorded in the source documents.

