If quasi-complete separation occurs due to low incidence of some OSCi levels then neighbouring OSCi levels may be pooled for the purpose of the analysis to a minimum of two levels ( $\leq 3$  and  $\geq 4$ ), in which case the analysis will simplify to a binary logistic regression. Also, covariates may be dropped from the analysis if it is clear that the cause of quasi-complete separation is a particular categorised covariate.

The proportional odds assumption will be tested by re-running the ordered logistic regression model with both unequal and equal slopes for the treatment effect and equal slopes for all other covariates.

Proportionality will be assessed by the statistical significance of the treatment effect for unequal slopes, at the 5% significance level.

The same analysis methods will be used to use to assess both of the estimands in [Section 9.3.1](#).

A sensitivity analysis of the estimand using the ITT population will be performed where OSCi levels of 0 and 1 will be derived based on the COVID-19 symptom assessments. An OSCi score of 0 will be assigned if no COVID-19 symptoms are present, regardless of the OSCi score recorded in the clinical database. An OSCi score of 1 will be assigned if any COVID-19 symptoms are present and an OSCi score of 0 was recorded in the clinical trial database. The number and percentage of patients with a rederived OSCi score will be presented at each time point along with the odds ratios and their 95% CIs and p-values.

The number and percentage of patients with each OSCi score at each post baseline visit will also be presented.

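### SAP 9.3.2.3: the rule that re-derives an OSCI score of 0 is not limited to recorded scores of 0 or 1, so read literally it relabels symptom-free patients with limited activities, or still in hospital, as uninfected

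*SAP*

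**What the plan says.** SAP section 9.3.2.3 analyses the OSCI at Days 7, 14, 21 and 28 by ordered logistic regression. It adds an ITT sensitivity analysis in which "OSCi levels of 0 and 1 will be derived based on the COVID-19 symptom assessments". Two rules follow:

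- For score 0: "An OSCi score of 0 will be assigned if no COVID-19 symptoms are present, regardless of the OSCi score recorded in the clinical database".
- For score 1: "An OSCi score of 1 will be assigned if any COVID-19 symptoms are present and an OSCi score of 0 was recorded" in the trial database.

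The SAP will report, at each time point, how many patients had a score re-derived, together with the odds ratios.

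Protocol section 6.6 defines the scale. Level 0 is "No clinical or virological evidence of infection". Level 3 is "Hospitalised, no oxygen therapy", and levels 4 to 7 are also inpatient states. From the day of discharge the score comes from two questions, one on symptoms and one on whether usual activities are back to their pre-COVID level. A patient with no symptoms whose activities have not returned scores 2.

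Symptoms are also assessed in hospital. The Days 1 to 14 list in protocol section 5.3.2, introduced by "For patients that remain in hospital the following assessments should be performed preferably in the following order", includes the COVID-19 symptom assessment. So does the Day 15 list in section 5.3.3. Section 5.3.4 continues it daily to Day 35, face to face for patients still in hospital. All four analysis days are covered.

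**The concern.** The evident purpose is to check the 0/1 boundary, which rests on one yes/no symptom question, against the fuller symptom assessment. That needs a rule confined to patients already at 0 or 1. The score-0 rule carries no such limit, and its closing clause sets the recorded score aside.

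If it is programmed as written, the checklist overrides two criteria that it does not measure: whether activities have returned (1 versus 2) and whether the patient is in hospital (2 versus 3 or more). A difference between this analysis and the main ordinal result could then come from the symptom split, from dropping the activity criterion, or from moving inpatients to the best category, and a reader could not tell which. Two programmers could also build different datasets from the same text.

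**Working it through.** The SAP gives no figure for this re-derivation, so there is none to reproduce. The check is a rule table, then a look at which cut-points can move, then an illustration of scale.

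**1. Rule table.** The literal rule is compared with one limited to recorded 0 or 1.

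| Recorded OSCI | No symptoms: literal rule | No symptoms: limited to 0/1 | Any symptom: both |
|---|---|---|---|
| 0 | 0 | 0 | 1 |
| 1 | 0 | 0 | 1 |
| 2 | 0 | 2 | 2 |
| 3 | 0 | 3 | 3 |
| 4 | 0 | 4 | 4 |
| 5, 6, 7 | 0 | unchanged | unchanged |

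The versions differ only for symptom-free patients recorded at 2 or above. In protocol 6.6, symptom-free with the answer No to "Usual activities returned to baseline level" is a 2; the literal rule makes it 0.

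**2. Cut-points.** A 0/1 re-split can move only the cut between 0 and 1 or above. The literal rule also moves the cut at ≤1 when a 2 becomes 0, and the cut at ≤2 when an inpatient becomes 0. It even reaches the SAP's fallback of two pooled levels (≤3 and ≥4), because a recorded 4 set to 0 crosses that line.

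**3. Scale at Day 28 (illustration only).** Protocol section 8.1 assumes 70% of placebo patients discharged and 30% recovered. Treating these sustained rates as Day 28 status, 70% − 30% = 40% sit at OSCI 2 (0.40 × 305 = 122). The other 30% (about 92 of 305) are not discharged, deaths included. Active-arm shares follow from 1 − (1 − p)^HR:

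- Protocol hazard ratios (discharge 1.45, recovery 1.7): discharged 1 − 0.30^1.45 = 0.825; recovered 1 − 0.70^1.7 = 0.455; at OSCI 2, 0.371.
- SAP section 6 simulation hazard ratios (discharge 1.7, recovery 1.35): discharged 1 − 0.30^1.7 = 0.871; recovered 1 − 0.70^1.35 = 0.382; at OSCI 2, 0.489.

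Let q2 be the symptom-free share at OSCI 2 and q3 the symptom-free share of those not discharged, equal in both arms. The documents give neither, so both are assumptions. After relabelling,

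P′(≤1) = P(≤1) + q2 × [P(≤2) − P(≤1)] + q3 × [1 − P(≤2)].

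For q2 = 50%, q3 = 0 and protocol hazard ratios: placebo 0.30 + 0.5 × 0.40 = 0.50; active 0.455 + 0.5 × 0.371 = 0.640; odds ratio (0.640/0.360)/(0.50/0.50) = 1.78.

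| q2 | q3 | Placebo at ≤1 | OR at ≤1, protocol HRs | OR at ≤1, SAP HRs |
|---|---|---|---|---|
| 0 | 0 | 30% | 1.95 | 1.44 |
| 25% | 0 | 40% | 1.81 | 1.53 |
| 50% | 0 | 50% | 1.78 | 1.68 |
| 75% | 0 | 60% | 1.83 | 1.99 |
| 25% | 10% | 43% | 1.72 | 1.42 |
| 50% | 10% | 53% | 1.70 | 1.57 |
| 50% | 25% | 57.5% | 1.60 | 1.43 |

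Under a 0/1 re-split the first row would hold throughout. At the ≤2 cut with protocol hazard ratios, the odds ratio goes from 2.03 to 1.99 (q3 = 10%) or 1.93 (q3 = 25%).

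**The case against.** The best defence is that the scope sentence confines the exercise to levels 0 and 1, so the closing clause of the score-0 rule means only whether a 0 or a 1 was recorded. On that reading the two rules are complete. This is possible, but the scope sentence names the levels to be produced, not the records eligible, and the closing clause waives any condition on the recorded score. The text is at best ambiguous.

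Moving a 2 to 0 might also be deliberate, since the descriptor of level 0 does not mention activities. A sensitivity analysis may depart from the main derivation, but the SAP does not state that aim, and it would not explain relabelling inpatients.

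Some stronger inferences are not supported:

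- **The difference between the two rules shows an error.** It does not. A recorded 1 with symptoms is already 1, so the score-1 rule needs to act only on a recorded 0.
- **The analysis breaches protocol 6.6, under which the score "must not be adjusted based on the results from other outcome assessments".** That sentence governs how the score is assessed and recorded. A labelled sensitivity analysis leaves the recorded score in place, and the fix below also uses the checklist.
- **The reported count of re-derived scores would be wrong.** It would correctly show what the rule did, so heavy relabelling would be visible, although the SAP does not ask for it by recorded level.
- **The effect is largest at Days 21 and 28.** The symptom-free share is not given at any visit. The inpatient pool is larger earlier: under the SAP's exponential placebo assumption, 0.30^(7/28) = 74% are undischarged at Day 7, against 30% at Day 28.

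**Conclusion.** The point holds as a defect of wording. Followed literally, the score-0 rule sets symptom-free patients recorded at 2 or above to 0, contrary to the protocol 6.6 algorithm, and the resulting odds ratio would not isolate the 0/1 split. The shift is two levels from a recorded 2 and up to seven from a recorded 7, against at most one in a true re-split.

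How many patients this touches cannot be known from the documents. Symptom-free patients on oxygen or ventilation may be few, so OSCI 2 is the likelier source. In the illustration every odds ratio at ≤1 stays above 1, but it falls in all rows with the protocol's hazard ratios and mostly rises with the SAP's, so the direction of distortion cannot be predicted. These figures rest on assumed symptom-free shares, equal across arms, and concern one cut rather than the fitted proportional-odds estimate.

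A reader might infer that the trial's efficacy conclusions are at risk. They are not. This is one sensitivity analysis of a secondary endpoint outside the testing hierarchy (protocol 8.5.4, SAP 7.6). The main ordinal analysis uses the recorded scores, and the primary and key secondary endpoints do not use the re-derived score.

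**What to change.** Replace the two re-derivation rules in SAP section 9.3.2.3 with: *Among assessments with a recorded OSCI of 0 or 1 and a non-missing symptom assessment, assign 0 if no COVID-19 symptom is present and 1 if any is present; recorded scores of 2 or above are not changed.*

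The non-missing condition is needed because the SAP does not say how an absent symptom assessment is treated, and a program could take it as no symptoms. The cost is one sentence in the SAP and the matching line in the program specification, with no new data and no change to any other analysis.

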#### **9.3.2.4 Change in total BCSS score**

Change in total BCSS score over the treatment period will be assessed by an MMRM.

Covariates will be included in the MMRM as per [Section 7.2](#), plus covariates for baseline total BCSS score, scheduled visit, an interaction term for treatment by visit and an interaction term for baseline total BCSS score by visit.

Also, estimates of the mean change ( $\pm 95\% \text{ CI}$ ) in total BCSS score as well as the estimated mean change ( $\pm \text{SE}$ ) in the individual BCSS scales over the treatment period as calculated by the MMRM analysis will be presented for SNG001 versus placebo in a panel plot.

Data from the follow-up visits or early withdrawal visits after day 15 will not be included in the analysis. The model will be fit for absolute score and change from baseline in score: the baseline BCSS covariate ensures that these models have identical treatment effects. Least Squares (LS) means for absolute scores and change from baseline scores and the LS mean difference between treatment groups will be presented for each post baseline visit up to day 15 and across the entire post baseline treatment period (day 2 – 15) with 95% CIs and p-values.

A covariance matrix will be used to account for the within patient correlation. If an unstructured matrix can be used this will be the first choice, otherwise a compound symmetry structure will be used. The

observed margin option will be used to ensure the model coefficients are weighted to reflect the actual proportions of each class level within the data.

Missing data will be handled as per [Section 7.3.2](#).

Absolute values and the change from baseline in total BCSS score will also be summarised over the entire study period.

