8.5.3 Analysis of Secondary Efficacy Endpoints

All analyses of secondary endpoints described below will include the covariates used for the primary analysis, unless stated otherwise.

Recovery and hospital discharge will be analysed at Days 7, 14, 21 and 28 using a logistic regression model to determine the difference in proportions for SNG001 versus placebo.

Improvement on the WHO OSCI scale will be analysed at Days 7, 14, 21 and 28 assessed using an ordered logistic regression model assuming proportional odds to estimate the odds ratios for SNG001 versus placebo. Adjacent WHO OSCi categories may be merged for some or all visits if the outcome frequency for some WHO OSCI levels is low for any treatment arm.

Observed WHO OSCI scores will also be summarised descriptively.

Change from baseline in breathlessness and cough scores according to the BCSS and total BCSS score will be assessed using a mixed model for repeated measures. The difference between SNG001 and Placebo across the treatment period (up to Day 14) will be estimated alongside the 95% CIs and p-values. The covariates used for the primary analysis will be used with an additional covariate for baseline score.

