## Statistical Analysis Plan (RotW)

Final v1.0, 08FEB2022

SG018

- High (> 66th percentile)

The following variables are factors of interest which have been selected so show homogeneity of the treatment effect:

- COVID-19 Related Therapy at randomisation
  - Remdesivir by any route
  - Corticosteroids by any systemic route (Dexamethasone, Methylprednisolone, Prednisolone, Hydrocortisone)
  - Dexamethasone by any route
  - Dexamethasone administered orally
  - Dexamethasone administered intravenously
- All cases of the above medication use will be included, regardless of whether indicated for COVID-19 or a comorbidity.
- SNG001 Manufacturing Batch
  - SNG001 manufactured using [REDACTED] derived material
  - SNG001 manufactured using [REDACTED] derived material.

The following covariates will be included in statistical models:

- Age as a continuous variable
- Sex:
  - Male
  - Female
- Prior duration of symptoms as a continuous variable
- Geographic region (See [Section 7.5](#))
- COVID-19 vaccine status at randomisation:
  - No prior COVID-19 vaccination
  - Partially vaccinated
  - Fully vaccinated

Patients who receive different types of COVID-19 vaccination will be pooled into a single subgroup.

Only subgroups with at least 20 patients in total will be included in any summaries or analyses.

For analyses of change from baseline for variables other than OSCI the baseline value will also be included as a covariate.

For subgroup analyses the subgroup variable will not be included in the models. The study has not been powered for any of the subgroups defined above, therefore all subgroup analyses should be considered exploratory.

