## Statistical Analysis Plan (RotW)

Final v1.0, 08FEB2022

SG018

			averaged over the whole study period
Change in breathlessness score over the study period	ITT	Treatment policy: Regardless of protocol deviations, treatment adherence and any concomitant therapies received for the treatment of SARS-CoV-2.	Difference in LS means between each SNG001 arm versus placebo
	Per Protocol	Hypothetical: Estimand for a situation with treatment compliance and no protocol deviations affecting efficacy.	averaged over the whole study period
Change in cough score over the study period	ITT	Treatment policy: Regardless of protocol deviations, treatment adherence and any concomitant therapies received for the treatment of SARS-CoV-2.	Difference in LS means between each SNG001 arm versus placebo
	Per Protocol	Hypothetical: Estimand for a situation with treatment compliance and no protocol deviations affecting efficacy.	averaged over the whole study period

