#### **9.3.2.5 *Change in breathlessness and cough scores***

Change in breathlessness and cough scores over the treatment period will be analysed using the same methods described for total BCSS score in [Section 9.3.2.4](#).

Absolute values and the change from baseline in breathlessness, cough and sputum score will be summarised over the entire study period. The change from baseline in each symptom score will also be summarised in shift tables.

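### If the unstructured BCSS model cannot be fitted, the SAP falls back directly to compound symmetry for 14 daily measures without a robust standard error, so per-visit intervals are miscalibrated whenever residual variance differs between days

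*SAP*

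**What the plan says.** SAP 9.3.2.4 gives one covariance rule for the BCSS mixed model: "If an unstructured matrix can be used this will be the first choice, otherwise a compound symmetry structure will be used". It does not define when an unstructured matrix counts as usable, and names no intermediate structure and no empirical standard error. Protocol 8.5.3 and 8.5.5 call for a mixed model for repeated measures but set no covariance rule.

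The model adjusts for baseline score and baseline-by-visit, as well as the SAP 7.2 covariates. Its output is both daily and averaged: "the LS mean difference between treatment groups will be presented for each post baseline visit up to day 15", and also "across the entire post baseline treatment period (day 2 – 15) with 95% CIs and p-values".

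SAP 9.3.2.5 carries the method over: "Change in breathlessness and cough scores over the treatment period will be analysed using the same methods described for total BCSS score". SAP Table 7 plans total BCSS in the ITT population only, but breathlessness and cough also in the per protocol population and in ITT subgroups. On subgroup size, SAP 7.2 says: "Only subgroups with at least 20 patients in total will be included in any summaries or analyses".

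The estimand is an average. SAP Table 23 defines the summary measure as a difference in LS means "averaged over the whole study period", and Protocol 8.5.3 says: "The difference between SNG001 and Placebo across the treatment period (up to Day 14) will be estimated alongside the 95% CIs and p-values".

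**The concern.** An unstructured matrix lets each day have its own variance and each pair of days its own correlation. Compound symmetry replaces all of that with one variance and one correlation. The standard error for any single day is then built from a variance pooled over all 14 days. If the true residual variance is not constant, that standard error is too small on some days and too large on others, and a larger sample does not cure it.

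Constant variance is doubtful here. Each BCSS item is bounded between 0 and 4 (Protocol 6.7), and patients are expected to improve and go home. SAP 7.3.2 also sets missing breathlessness to 4 when the OSCI score is 5 or above, which adds extreme values on some days. At stake are the daily CIs and p-values for three scores.

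**Working it through.** The documents give no SD, correlation or coverage figure for BCSS by day, so there is no stated figure to reproduce. All SDs and correlations below are assumptions.

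**Size of the matrix.** Days 2 to 15 are 15 − 2 + 1 = 14 visits. Unstructured needs 14 × 15 / 2 = 105 covariance parameters; compound symmetry needs 2.

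**Formula (complete data).** The compound-symmetry standard error on day t uses SD_pooled = √(mean of SD_t²), so

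coverage on day t = 2Φ(1.96 × SD_pooled / SD_t) − 1.

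**Step 1: assumed SDs used directly as residual SDs, linear over 14 visits.**
- SD 2.4 falling to 1.2: mean of SD² = 1.8² + (1.2/13)² × 16.25 = 3.378, so SD_pooled = 1.838. Standard-error ratios are 1.838/2.4 = 0.77 and 1.838/1.2 = 1.53. Coverage is 86.7% on the first day and 99.7% on the last.
- SD 2.0 falling to 1.6: SD_pooled = 1.804; coverage 92.3% and 97.3%.
- By ratio of largest to smallest SD, coverage on the highest-variance day is 92.3% (ratio 1.25), 90.0% (1.5), 86.7% (2) and 82.9% (3). The type I error there is 7.7%, 10.0%, 13.3% and 17.1%.

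**Step 2: allow for the baseline adjustment that the SAP specifies.** With AR(1) correlation ρ and baseline one day before Day 2, the residual SD at visit k (k = 1 to 14) is SD_k × √(1 − ρ^(2k)). The Step 1 formula is then applied to these residual SDs. For example, with ρ = 0.9 the Day 2 residual SD is 2.4 × √(1 − 0.81) = 1.05.

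| Assumed SD | ρ | Day 2 | Day 15 | Lowest (day) |
|---|---|---|---|---|
| 2.4 to 1.2 | 0.5 | 91.1% | 99.7% | 88.6% (3) |
| 2.4 to 1.2 | 0.7 | 95.3% | 99.5% | 89.8% (4) |
| 2.4 to 1.2 | 0.9 | 99.3% | 98.5% | 91.7% (6–7) |
| 2.4 to 1.2 | 0.95 | 99.8% | 97.3% | 92.1% (8) |
| 2.0 to 1.6 | 0.7 | 98.2% | 96.6% | 93.3% (5) |
| 2.0 to 1.6 | 0.9 | 99.9% | 93.9% | 92.9% (10) |
| 2.0 to 1.6 | 0.95 | >99.9% | 91.7% | 91.6% (14) |

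Measurement error weakens the link to baseline. If the baseline correlation is 0.6 to 0.8 times 0.9^k, Day 2 coverage for SD 2.4 to 1.2 is 90.3% to 94.1%. The same weakening with SD 2.0 to 1.6 leaves the lowest day at about 94%. If SD rises instead (1.2 to 2.4, ρ = 0.9), the Day 15 residual SD is 2.34 against a pooled 1.64, and Day 15 coverage is 83%. So the worst day can fall early, in the middle or late.

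**Step 3: simulation with dropout.** There were 1,000 trials per scenario with 305 per arm, a REML compound-symmetry fit, visit-by-treatment means and AR(1) correlation 0.9 where SD changes. Dropout followed Protocol 8.1 (25% over 28 days, so 1 − 0.75^(14/28) = 13.4% by 14 days). Baseline and other covariates were left out. Monte Carlo error near 95% is √(0.95 × 0.05/1000) = 0.7 points.

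| Scenario | Model-based Day 2 | Model-based Day 15 | Model-based average |
|---|---|---|---|
| True compound symmetry, constant SD | 95.8% | 94.9% | 95.2% |
| AR(1), constant SD | 95.6% | 93.8% | 95.1% |
| SD 1.6 to 2.0 | 96.6% | 90.5% | 94.5% |
| SD 1.4 to 2.1 | 99.1% | 88.8% | 94.8% |
| SD 1.2 to 2.4 | 99.7% | 86.0% | 94.5% |
| SD 2.4 to 1.2 | 87.1% | 99.6% | 94.9% |

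With sandwich standard errors on the same fits, coverage at Days 2, 8 and 15 was 94.2% to 96.3% in every changing-SD scenario, and 94.4% to 95.0% for the average. Changing variance does the damage; a wrong correlation shape alone (row 2) does little. The average holds because, with complete data, compound symmetry estimates the mean variance and mean covariance, and these are all that the variance of an average needs.

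**Step 4: how likely is the fallback?** In the full ITT set, 105 parameters against about 610 patients with daily data may well be estimable. In a subgroup of 20, counting intercept, treatment, age, sex, symptom duration, region (2), vaccine status (2) and baseline leaves 20 − 10 = 10 degrees of freedom. Counting only the terms that vary by visit (intercept, treatment, baseline) leaves 20 − 3 = 17. An unstructured matrix needs 14, so before any missing data it can already be out of reach.

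**The case against.** The case for leaving the text alone has four parts.

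- **The estimand is unharmed.** Table 23 and Protocol 8.5.3 both target a period average, and its coverage stayed near 95%. BCSS is outside the testing hierarchy of SAP 7.6. This stands, and it limits the point to supplementary daily intervals.
- **The fallback may never be used in the main analysis.** Total BCSS is modelled in the ITT set only, and visit interactions add mean parameters, not covariance parameters. This stands for the full ITT set. It does not stand for small breathlessness and cough subgroups, though SAP 7.2 labels all subgroup analyses exploratory.
- **The rule is pre-specified and contradicts nothing in the protocol.** True, but when unstructured counts as usable is left open, and pre-specification does not repair a standard error built on the wrong variance.
- **Sandwich standard errors are weakest in small subgroups, where the fallback is likeliest.** This stands and is dealt with in the fix.

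A reader might infer that, because patients recover and scores shrink, daily intervals must be too narrow early and too wide late, with about 87% coverage on the first day. The documents do not support this. They give no SD by day, and the model adjusts for baseline and baseline-by-visit. Early scores are usually closest to baseline, so early residual variance may be the smallest. For both falling-SD patterns with ρ from 0.7 to 0.95, Day 2 coverage was at or above nominal. Weaker baseline correlation did leave early undercoverage, so neither direction is established.

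**Conclusion.** The point holds as a conditional one. If the fallback is used and residual variance differs across days, per-visit 95% CIs and p-values are too narrow on high-variance days and too wide on low-variance days. For the falling-SD patterns examined, the lowest per-visit coverage is about 87% to 93% (94% in the mildest) and the highest is above 99% in most cases. Rising SDs or a threefold SD ratio take the lowest to about 83%. These sizes rest on assumed linear SD changes and assumed correlations. The coverage figures with baseline adjustment also assume complete data, and the simulation with dropout omits baseline.

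A reader might also conclude that the BCSS result as a whole would be unreliable. That does not follow: the averaged contrast keeps its coverage, and the primary and key secondary conclusions do not depend on this model. This is a cheap improvement, not a flaw that threatens the trial.

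**What to change.** In SAP 9.3.2.4, replace the single fallback with a pre-specified sequence: if the unstructured model does not converge, use the first structure that does among heterogeneous Toeplitz, heterogeneous AR(1) and compound symmetry. State the convergence criterion. Use empirical (sandwich) standard errors for any structure other than unstructured. Where an analysed set is too small for these to be reliable, use a small-sample-corrected version or present only descriptive per-visit summaries. Section 9.3.2.5 inherits the change by its cross-reference.

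The cost is a few lines of SAP text and standard software options. The downsides are slightly larger standard errors in some cases and less dependable sandwich standard errors in small samples. The sandwich part was checked by simulation at 305 per arm; the heterogeneous structures were not simulated, but they remove the equal-variance assumption directly.
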